### 6.2. AIM 1 EXPLORATORY ANALYSIS

An exploratory analysis will compare risk between participants in Aim 1, Group A who did and did not receive SAP (BPG) during the GOAL Trial. In order to do this comparison, we will “reconstruct” or emulate a longer trial, in essence analysing the data as if the GOAL Trial originally had longer follow-up planned. This will follow the framework of target trial emulation for the design and analysis of observational studies that involves precisely specifying the protocol of the target trial and then emulating each component of the protocol with observational data (1).

Our target trial (which we will call the **Target-GOAL Trial**) would have randomized participants to the following groups at the start of the GOAL Trial. Each group represents a treatment algorithm, with a predetermined change at 2 years based on the results of an echocardiogram done at 2 years (in our case, at the end of the GOAL-Trial).

Randomized groups at the start of the Target-GOAL Trial:

- Treat with BPG for 2 years. Assess with echocardiogram after 2 years. If normal at the end of 2 years, stop treatment. If latent disease is present then treat with BPG for 3 years.
- Do not treat with BPG for 2 years. Assess with echocardiogram after 2 years. If normal at the end of 2 years no change. If latent disease is present then treat with BPG.

Randomized at the start of the GOAL Trial to one of the following interventions	2 years post randomization	Echocardiogram done – RHD status assessed	Intervention for 3 years	5 years after randomization
BPG	- Normal - Latent RHD - Severe	→ No treatment → Treat with BPG → Outcome: RHD		Echocardiogram done – RHD status assessed
Control	- Normal - Latent RHD - Severe	→ No treatment → Treat with BPG → Outcome: RHD		Outcome

Figure 2: Groups randomized to at the start if the Target-GOAL Trial

This study design answers, from a randomized comparison, the following question: What is the impact of treatment with BPG for 2 years, after which participants with a normal echocardiogram stop treatment, and participants with latent RHD start treatment, compared to no treatment in the initial 2 years, 5 years after initial diagnosis of latent RHD.

The primary study outcome is development of RHD on the side by side comparison. Participants with confirmed ARF and who develop echocardiographic evidence of RHD at any time during the study period will be counted as having reached the primary study endpoint (development of RHD).

We will report the proportion of children who develop echocardiographic evidence of RHD in each of the “randomized” groups in Target-GOAL. We will fit a GLM with an identity link and binomial distribution, adjusted for stratification variables in GOAL (RHD category borderline or definite), to estimate the difference in proportion of children who develop echocardiographic evidence of RHD, with a 95% CI, between the two “randomized” arms.

We will also report the proportion of participants with RHD in each of the following groups:

- SAP for 2 years, no latent RHD, no treatment
- SAP for 2 years, latent RHD, SAP
- Control for 2 years, no latent RHD, no treatment
- Control for 2 years, latent RHD, SAP

Given that there will be a larger proportion of missing data for this Target-GOAL trial, we will do the analysis with all the data we have (available case analysis) and also repeat the analysis using multiple imputation to adjust for the missing outcome data. We will assume that the missing data is missing at random. We will use the Multiple Imputation by Chained Equations (MICE) method using a Gibbs-like algorithm to impute multiple variables sequentially using univariate fully conditional specifications. We will include the outcome variable, treatment arm, stratification variable and appropriate baseline variables from the GOAL trial in the imputation model.

### 6.3. AIM 2

We will determine the proportion of children with RHD progression and regression at 5 years among children with persistent latent RHD who receive every-4-week BPG prophylaxis and present this proportion with a

95% CI interval. An exploratory sub-analysis will compare risk between participants in Aim 2 who did and did not receive SAP during the GOAL Trial.

We will calculate the rate of progression and regression at the end of GOAL-Post in the following groups of participants:

- Randomized in the GOAL Trial to SAP and latent RHD at the start of GOAL-Post.
- Randomized in the GOAL Trial to control and latent RHD at start of GOAL-Post. These participants did not receive SAP in the GOAL Trial but did receive SAP in GOAL-Post.

Additional

- Randomized in the GOAL Trial to SAP and normal echocardiogram (no latent RHD) at the 2-year endpoint of the GOAL Trial and at the start of GOAL-Post. (Children who had SAP for two years and are then taken off SAP given a normal echocardiogram and no sign of latent RHD.)
- Randomized in the GOAL Trial to control and normal echocardiogram (no latent RHD) at the 2-year endpoint of the GOAL Trial and at the start of GOAL-Post, these participants never received SAP.
- Normal at the end of the GOAL Trial, regardless of randomized treatment arm

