### 3. BACKGROUND/INTRODUCTION

The GOAL Trial reached completion in October 2020, finding that SAP resulted in a significant and substantial reduction in RHD progression among children with latent, or screen-detected RHD. These data have important clinical and public health implications. However, the GOAL Trial also showed that approximately 50% of children with latent RHD regressed at two-years, with the majority (85%) returning to a normal echocardiographic study with or without antibiotic prophylaxis. These results raise questions on the recommended duration of prophylaxis for latent RHD, with no current evidence to guide practice for this group.

GOAL-Post is two prospective extension studies that build on the infrastructure (case managers and peer groups) and success (98% retention and 99% BPG adherence) of the GOAL Trial.

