### **3.3. STUDY POPULATION**

**Aim 1** planned to enrol between 953 and 1102 participants, a maximum of 364 participants with normal echocardiograms after 2-years of participation in the GOAL Trial (Group A) and an appropriate number of age and sex matched controls (Group B, see sample size) without echocardiographic evidence of RHD.

**Group A:** Children and adolescents were eligible for Aim 1 if they

- (1) are a prior GOAL Trial participant deemed by the adjudication panel to have a normal echocardiogram at the 2-year endpoint,
- (2) are not receiving SAP, and
- (3) agree to participate in the study via the study's informed consent/assent process.

**Group B:** Children and adolescents were eligible for Aim 1 if they

- (1) have a normal echocardiogram at the start of the study,
- (2) meet the age and sex match requirement (from former GOAL Trial participants), and
- (3) have agreed to participate in the study via the study's informed consent/assent process.

**Aim 2** planned to enrol up to 415 participants with persistent latent RHD after 2 years of participation in the GOAL Trial. Children and adolescents were eligible for Aim 2 if they

- (1) were a prior GOAL Trial participant deemed by the adjudication panel to have persistent latent RHD on echocardiogram at the 2-year endpoint,
- (2) have been prescribed SAP (BPG), and
- (3) agree to participate in the study via the study's informed consent/assent process.

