## 4. POPULATIONS OF ANALYSIS

For **Aim 1** the analysis population will be all participants enrolled in Aim 1 in GOAL-Post. The Aim 1 Group A population is defined as GOAL-Post consent completed, arm 1 selected, and GOAL-Post enrolment echo is normal. The Aim 1 Group B population is defined as GOAL-Post consent completed and arm 4 selected.

For **Aim 2** the analysis population will be all participants enrolled in Aim 2 in GOAL-Post. The Aim 2 population is defined as GOAL-Post consent completed and arm 2 selected, or GOAL-Post consent completed, arm 1 selected, and GOAL-Post enrolment echo is not normal.

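### Section 6.2 announces a Group A comparison by prior prophylaxis, but the Target-GOAL analysis offered for it compares two strategies in all randomised children and identifies no Group A difference

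*SAP*

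**What the plan says.** The plan abbreviates secondary antibiotic prophylaxis as SAP; I write prophylaxis here so that SAP is not used in two senses.

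- **Announced comparison (section 6.2, first sentence).** An exploratory analysis "will compare risk between participants in Aim 1, Group A who did and did not receive SAP (BPG) during the GOAL Trial".
- **Stated means (section 6.2, next sentence).** It begins "In order to do this comparison, we will" and goes on to describe emulating a GOAL Trial with longer follow-up.
- **Who is in Group A.** Section 3.3 requires that children "are a prior GOAL Trial participant deemed by the adjudication panel to have a normal echocardiogram at the 2-year endpoint". Section 4 adds a condition at entry to the extension: "The Aim 1 Group A population is defined as GOAL-Post consent completed, arm 1 selected, and GOAL-Post enrolment echo is normal".
- **Who is in Target-GOAL.** The target trial "would have randomized participants to the following groups at the start of the GOAL Trial". Figure 2 of section 6.2 gives each arm three branches at two years: normal, latent RHD and severe.
- **What is modelled.** A binomial GLM with identity link, adjusted for baseline RHD category, is fitted "to estimate the difference in proportion of children who develop echocardiographic evidence of RHD, with a 95% CI", between the two whole arms. Table 6 reports this difference.
- **What is reported on normalised children by GOAL arm.** Section 6.2 lists separate proportions, and Table 5 gives each with its own confidence interval.

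**The concern.** The opening sentences of 6.2 tie the Target-GOAL result to a question about children who had normalised at two years: does their later risk differ according to whether they had received prophylaxis? The model answers another question: how do two treatment rules, applied from randomisation to every child, compare at five years? Population, time zero and event window all differ between the two.

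This matters because the plan's clinical question in section 2.1 concerns stopping prophylaxis in children who normalise. If the Table 6 difference is reported under the opening sentence of 6.2, a contrast driven by children outside Group A, or by early events, could be presented as evidence about those who normalised. A null result could likewise conceal a difference among them.

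**Working it through.** No figure of the plan's own needs reproducing here. The check sets the two comparisons side by side, then uses the plan's counts and a short illustration.

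**1. The two comparisons**

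| Feature | Announced (6.2, first sentence) | Modelled (6.2 and Table 6) |
|---|---|---|
| Population | Group A: normal at two years | All randomised: normal, latent and severe at two years |
| Start of follow-up | After the two-year echocardiogram | GOAL randomisation |
| Events | Those arising in children normal at two years | Events at any time in the study period; severe at two years counts as the outcome |
| Contrast | Prophylaxis v none within Group A | Arm v arm, whole strategy |

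**2. Is the Group A contrast specified elsewhere?**
- Section 6.2 (list of four groups) and Table 5: a proportion per group, no difference.
- Table 3, BPG-arm rows: BPG-arm children against Group B, not against control-arm children who normalised.
- Table 7, additional rows: again one line per group.
- For Aim 2, by contrast, section 6.3 announces the parallel comparison and Table 7 has a row for its risk difference and p-value. Aim 1 has no such row.

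**3. Share of Group A**

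Inputs from sections 3.3 and 3.4: at most 364 children normal at two years, and 415 with persistent latent RHD.

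364 / (364 + 415) = 364 / 779 = 46.7%

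415 / 779 = 53.3%

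So more than half of the children counted are outside Group A, before adding any who were severe at two years or are not counted in these two figures.

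**4. Does the whole-arm difference identify the Group A difference?**

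Arm risk = (share normal × their risk) + (share latent × their risk) + share with RHD by two years.

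All shares and risks below are assumed for illustration. The plan gives none of them by arm. The later risk in latent children is set at 10% in both arms.

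| Case | BPG arm | Control arm | Whole-arm difference | Difference in normals |
|---|---|---|---|---|
| a | 0.49×0.03 + 0.50×0.10 + 0.01 = 0.0747 | 0.45×0.03 + 0.47×0.10 + 0.08 = 0.1405 | −6.58 points | 0 |
| b | 0.49×0.05 + 0.50×0.10 + 0.01 = 0.0845 | 0.45×0.02 + 0.47×0.10 + 0.08 = 0.1360 | −5.15 points | +3 points |
| c | 0.47×0.05 + 0.51×0.10 + 0.02 = 0.0945 | 0.47×0.02 + 0.48×0.10 + 0.05 = 0.1074 | −1.29 points | +3 points |
| d | 0.47×0.05 + 0.53×0.10 = 0.0765 | 0.47×0.02 + 0.53×0.10 = 0.0624 | +1.41 points | +3 points |

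The same +3 points among normalised children goes with whole-arm differences from −5.15 to +1.41. Case a shows a sizeable whole-arm difference with none among normalised children.

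**The case against.** The best reply is that the plan does say what Target-GOAL estimates. Section 6.2 describes each arm as a treatment rule with a planned change at two years, draws all three branches, and states the strategy question in full. Table 6 is titled as the Target-GOAL outcome, and its footnotes spell out the latent branch in both arms. Group A results by earlier prophylaxis are also already planned as proportions in Table 5. All of this is correct, and it limits the fault to the opening of 6.2 and to the absence of any defined Group A contrast. It does not remove the fault: the section states two purposes and links them as if they were one. Subtracting the Table 5 proportions informally would also compare groups selected on a status observed after randomisation, and the plan does not say so.

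Three stronger readings are tempting but not supported.

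- A reader might infer that Target-GOAL is an invalid analysis. It is not; it is a reasonable design for the strategy question.
- A reader might infer a calculable chance that Table 6 reaches significance when nothing differs after two years. The plan gives no two-year risks by arm, so any such probability rests on invented inputs. Nor would it be an error rate: a strategy contrast that detects a real early benefit is working as intended.
- A reader might infer that the benefit GOAL has already reported passes wholesale into Table 6. Section 3 reports that "SAP resulted in a significant and substantial reduction in RHD progression among children with latent, or screen-detected RHD", but Figure 2 sends only severe children to the outcome at two years. Section 6.2 defines the outcome both by side-by-side comparison and by events at any time. Some overlap is likely; its size cannot be fixed from this document.

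**Conclusion.** The point holds as a mismatch of estimands. Section 6.2 promises a comparison within Group A and specifies a five-year comparison of strategies over all randomised children. Group A is at most 47% of the children counted, and the whole-arm difference determines neither the size nor the sign of a Group A difference. That conclusion follows from the definitions; the assumed risks in the illustration only make it visible.

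Importance is low to moderate. The analysis is labelled exploratory, no sample size or decision rule depends on it, and the Aim 1 primary analysis against Group B, with its BPG-arm repeat, is untouched.

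**What to change.** 1. Reword the first two sentences of 6.2 so that Target-GOAL is described as a comparison of two treatment strategies in all randomised GOAL participants, and not as the means of comparing Group A by prior prophylaxis.
2. For Group A by prior prophylaxis, choose one of two options:
   - keep the two planned proportions and label them descriptive only; or
   - add one exploratory row giving the risk difference with 95% CI, adjusted for baseline RHD category, parallel to the Aim 2 row in Table 7. Label it non-randomised, because normal status at two years is observed after randomisation.
3. Optionally, split the Table 6 events into those present by the two-year echocardiogram and those first seen later. This helps in reading the strategy result but gives no Group A information, since later events still pool normalised and latent children.

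The cost is wording and at most one table row, from data already held. The downside is that the Group A contrast loses any claim to be a randomised effect estimate. An added row would also be imprecise. Assume an equal split of the maximum Group A between GOAL arms, 10% loss (364 × 0.9 / 2 ≈ 164 per arm) and the plan's 3% risk in both. The unadjusted 95% CI half-width is then 1.96 × √(2 × 0.03 × 0.97 / 164) ≈ 3.7 points, which is a reason to keep the row exploratory.

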## 5. OUTCOME VARIABLES

All Aim 1 echocardiograms will undergo blinded review by a panel of 2 cardiologists (2012 WHF guidelines), consisting of pre-review by 2 of these cardiologists (to guide discussion) and final consensus determination by the panel. A side-by-side comparison of the echo done at the end of the GOAL Trial and the end of GOAL-Post will also be done. Echocardiograms will be reviewed with side-by-side two-year (completion of the GOAL Trial) and five-year (end of GOAL-Post) echocardiograms presented to the panel, with random right or left display. The panel will be blinded to timing of the echocardiograms and will determine if the studies were “the same”, “right worse” or “left worse” by application of strict operational definitions, defined in the GOAL Trial.

The primary outcome of **Aim 1** will be development of echocardiographic evidence of RHD (2012 WHF Criteria) among children and adolescents with a normal echocardiogram at the 2-year endpoint in the GOAL Trial and upon enrolment into GOAL-Post (variable enollecho).

An **alternative outcome** for **Aim 1** is worsening on a side-by-side comparison of the echo done at the end of the GOAL Trial and the end of the GOAL-Post trial. These will be assessed as same, progressed or regressed. This is done only for Group A. This is captured in the database as a combination of two variables. If eligible\_echo\_comparison is “no” then the result is “same”. If eligible\_echo\_comparison is “yes” then the result is captured in the variable side\_by\_side results. The final diagnosis is given as the variable final\_diagnosis\_after\_comparison. Again this variable is a combination of two variables . If eligible\_echo\_comparison is “no” then the result is “normal”.

The primary outcome of **Aim 2** will be echocardiographic progression and regression among children who had persistent latent RHD at the end of the GOAL Trial. This will be variable enollecho from Period 26.

Progression is defined as progression of echocardiographic features of latent RHD to include:

- New pathological regurgitation at a previously unaffected valve
- Worsening grade of existing mitral or aortic regurgitation (mild, moderate, severe)
- Development of two morphological features consistent with RHD (2012 WHF criteria) at a valve that previously had normal morphology or the addition of one morphological feature at a valve previously only showing a single morphological abnormality.

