## Statistical Analysis Plan

**Table 6: Primary outcome of Target-GOAL Trial (Progression on side by side echo)**

	BPG + Proportion (95% CI)	Control + Proportion (95% CI)	Difference (95% CI)	p-value
Available case analysis				
Analysis using multiple imputation				

BPG +: Treat with BPG for 2 years. Assess with echocardiogram after 2 years. If normal at the end of 2 years, stop treatment. If latent disease is present then treat with BPG for an additional 3 years.

Control +: Do not treat with BPG for 2 years. Assess with echocardiogram after 2 years. If normal at the end of 2 years no change. If latent disease is present then treat with BPG for 3 years.

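### The exploratory Target-GOAL comparison includes children with latent RHD at year 2, but its side-by-side outcome is stated only for Group A and no rule links the Aim 2 outcome to it

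*SAP*

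**What the plan says.** Below, SAP means the analysis plan, except inside a quotation, where it means secondary antibiotic prophylaxis.

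**Population.** Section 6.2 opens by saying that the exploratory analysis will "compare risk between participants in Aim 1, Group A who did and did not receive SAP (BPG) during the GOAL Trial". It then describes a target trial that "would have randomized participants to the following groups at the start of the GOAL Trial". Both treatment algorithms cover children who are normal and children who have latent RHD at year 2, and Figure 2 places the outcome "5 years after randomization". The four result groups listed later in section 6.2 include the latent group of each arm.

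**Outcome.** Section 6.2 states: "The primary study outcome is development of RHD on the side by side comparison". The table shell repeats the method under another label: "Primary outcome of Target-GOAL Trial (Progression on side by side echo". A further sentence adds events: "Participants with confirmed ARF and who develop echocardiographic evidence of RHD at any time during the study period will be counted as having reached" the endpoint.

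**Where the reading exists.** Section 5 describes it thus: "Echocardiograms will be reviewed with side-by-side two-year (completion of the GOAL Trial) and five-year (end of GOAL-Post) echocardiograms presented to the panel". Under the Aim 1 alternative outcome it adds: "This is done only for Group A". Sections 3.3 and 4 define Group A as children who were normal at the end of GOAL and on the GOAL-Post enrolment echo.

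**Outcome for the other children.** Section 5 gives Aim 2 its own outcome, progression and regression by WHF category, taken from the variable enollecho at Period 26. Table 7 reports it.

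**Missing data.** Section 6.2 plans an available-case analysis and multiple imputation. The variables listed for imputation are outcome, arm, stratum and suitable GOAL baseline variables.

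**The concern.** The population is everyone randomised in GOAL, while the outcome is a reading stated only for those who were normal two years later. Section 6.2 presents its answer as coming from a randomised comparison. That holds if the endpoint is determined in the same way for every randomised child. It does not hold if the endpoint exists only for children in a particular state at year 2, because that state arises after randomisation. Section 3 reports that prophylaxis reduced progression in GOAL, so year-2 state cannot be assumed independent of arm.

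The endpoint also has three descriptions: development of RHD (text), progression (Table 6) and RHD status at 5 years (Figure 2). Every child entered GOAL with borderline or definite disease, so these are different events. Unless one is fixed beforehand, the choice could be made after the data are seen.

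**Working it through.** The SAP gives no figure of its own to reproduce here. The check sets the passages side by side and counts the children affected.

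**1. Does any passage extend the side-by-side reading to Aim 2?** No. Section 5 introduces the panel review for Aim 1 echocardiograms and limits the side-by-side reading to Group A. Sections 6.3 and Table 7 use progression and regression for Aim 2 without mentioning it.

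**2. Does any rule map the Aim 2 outcome to the Target-GOAL endpoint?** No. Section 6.2 does not mention enollecho or Period 26.

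**3. How many children are affected?**

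- From section 3.4: at most 364 in Group A, and 415 with persistent latent RHD. 364 + 415 = 779, and 415 / 779 = 53.3%.
- With the smallest planned Group A (291): 291 + 415 = 706, and 415 / 706 = 58.8%.
- From section 3: about 50% regressed, and 85% of those became normal. Normal at year 2: 0.50 × 0.85 = 42.5%. Not normal: 1 − 0.425 = 57.5%.
- Assuming that approximately 50% means 45% to 55%: 0.45 × 0.85 = 38.25% and 0.55 × 0.85 = 46.75% normal, so 61.75% and 53.25% not normal.

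These are head counts. The counts of 364 and 415 are ceilings and do not include children with severe disease at year 2, so they do not partition the target trial exactly.

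**4. Do the candidate endpoints agree?** Four illustrative paths (entry, year 2, year 5):

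| Path | Year 2 against year 5, if read | Progression from entry category | Any RHD at year 5 |
|---|---|---|---|
| Borderline, normal, borderline | Worse | No event | Event |
| Borderline, borderline, borderline | Same | No event | Event, unless unchanged latent RHD is excluded |
| Borderline, definite mild, definite mild | Same | Event | Event |
| Borderline, normal, normal | Same | No event | No event |

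Three of the four paths are classified differently depending on the definition. The third shows that a change in years 0 to 2 short of severe disease lies outside the side-by-side reading.

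**5. Does the any-time clause close the gap?** Only in part. It plausibly reaches back to GOAL entry, but it gives no reference state for a child who already has borderline or definite RHD. Its wording can also be read as requiring ARF together with echo evidence, whereas section 6.1 counts each separately.

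**6. Does the imputation close it?** Not as listed. If outcomes are observed mainly in children normal at year 2, values for the others would be modelled on those children, with no year-2 category in the model to tell them apart.

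**7. Related table shell.** Table 3 has Group B, difference and p-value cells under its side-by-side rows. Group B does not receive that reading, and section 6.1 only promises a summary of it.

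**The case against.** Three stronger readings are tempting, and the SAP supports none of them.

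- *Children with latent RHD at year 2 have no outcome.* They do: a final-visit echo (section 3.5), enollecho at Period 26 and category-change definitions (section 5), and Table 7. What is missing is a side-by-side reading, or a rule linking that outcome to Target-GOAL.
- *The SAP restricts Target-GOAL to children normal at year 2.* Section 6.2 says that all available data will be used and lists both latent groups for reporting. Restriction follows only if the stated outcome is taken literally; it is one result of an ambiguity.
- *The coding in section 5 shows that the reading cannot apply to latent cases.* Only one branch does. A child marked as not eligible for comparison is set to unchanged and to a normal final diagnosis, which cannot both be right for a child with latent RHD at year 2. A child marked as eligible avoids those defaults, and the SAP does not give the eligibility rule.

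It is also fair to say that the limitation to Group A sits in an Aim 1 paragraph and may only be a contrast with Group B, that the any-time clause and the severe branch of Figure 2 capture some early events, and that the imputation list is not said to be exhaustive.

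These points narrow the concern but do not remove it. Even on the generous reading, no passage extends the side-by-side comparison to Aim 2, and the endpoint still has three labels and no reference state.

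**Conclusion.** The contradiction stands in this form: the Target-GOAL comparison covers all randomised children, its endpoint is a reading stated for Group A only, and nothing connects the Aim 2 outcome to that endpoint. About 53% of the planned maximum counts are affected (59% with the smallest planned Group A), or about 57.5% from the background figures (53% to 62% under the assumed range).

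If the outcome is followed as written, the available-case comparison rests mainly on children normal at year 2, and the listed imputation variables do not correct for that selection. A reader might infer that the result is biased towards one arm. The SAP gives neither normalisation by arm nor outcome risks by year-2 state, so neither the direction nor the size of any bias can be derived.

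The analysis is exploratory and the Aim 1 primary analysis is unaffected. The point should be settled before analysis because it decides which children and which events are compared.

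**What to change.** 1. In section 6.2 and Table 6, define one endpoint from the WHF category diagnosis available for all randomised children at year 2 and year 5. Name the variable and period for Group A as well as Aim 2, since section 5 gives a year-5 period only for Aim 2.
2. Fix the reference before analysis and state what it does to the question. Progression from the GOAL entry category does not count a recurrence that only returns to that category, although recurrence after a normal echo is central to Aim 1. RHD status at year 5 counts unchanged latent RHD unless this is excluded. The sponsor should choose; reporting the four year-2 groups alongside shows what the choice hides.
3. Keep the side-by-side result as a descriptive Group A summary (section 6.1, Table 4).
4. Add year-2 echo category to the imputation model.
5. Reconcile the ARF clause in section 6.2 with section 6.1, where ARF and echo evidence each count.
6. In Table 3, remove the Group B, difference and p-value cells under the side-by-side rows.

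The cost is wording in section 6.2 and two table shells, with no new data collection evident from the SAP. The main downside is that the endpoint may combine readings made by different methods, because blinded panel review is stated only for Aim 1 echocardiograms. The Aim 2 reading method should be confirmed and reported with the result.

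### Target-GOAL starts at GOAL randomisation, but its side-by-side outcome takes the year-2 echo as reference and is defined only for children who were normal at year 2

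*SAP*

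**What the plan says.** Section 6.2 places time zero at GOAL entry: Target-GOAL "would have randomized participants to the following groups at the start of the GOAL Trial". Its question is the effect of two initial years of BPG "compared to no treatment in the initial 2 years, 5 years after initial diagnosis of latent RHD". Both arms contain children who were normal and children who were latent at year 2; Figure 2 sends the latent ones to BPG and marks only the Severe category at year 2 as an outcome.

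The outcome sentence is "The primary study outcome is development of RHD on the side by side comparison", and Table 6 repeats it in its title: "Primary outcome of Target-GOAL Trial (Progression on side by side echo". The sentence that follows in 6.2 adds confirmed ARF and participants "who develop echocardiographic evidence of RHD at any time during the study period will be counted as having reached the primary study endpoint".

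Section 5 describes the reading itself: "Echocardiograms will be reviewed with side-by-side two-year (completion of the GOAL Trial) and five-year (end of GOAL-Post) echocardiograms presented to the panel". In defining this outcome it adds: "This is done only for Group A". No comparison of the GOAL enrolment echo with the year-5 echo appears anywhere in the plan.

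Section 5 also requires progression to be a change of diagnostic category, and lists borderline to definite mild as one such change. Section 6.2 gives the GOAL stratification variable as borderline or definite RHD, so every randomised child had one or the other at entry.

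**The concern.** A comparison that starts at randomisation needs an outcome measured from randomisation. Here the reference image is taken two years later, after the treatment under study has had its chance to work. Section 3 reports that prophylaxis substantially reduced progression over those two years. An outcome anchored at year 2 cannot show that reduction, except through the year-2 Severe category or through a favourable reading of the any-time clause.

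The restriction to Group A adds a second problem. Being normal at year 2 is itself a result of the first two years. If only those children have a side-by-side reading, the available-case version of this outcome rests largely on a group selected after randomisation. Multiple imputation would then have to fill in latent children with no observed side-by-side readings of their own kind to learn from. What is at stake is whether Table 6 can be described as a randomised comparison.

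**Working it through.** The plan gives no sample size, power or event figure for Target-GOAL, so there is nothing to reproduce. The check traces paths through the stated rules and adds simple arithmetic.

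**Paths**

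| Entry | Year 2 | Year 5 | Change from entry | Result under section 5, section 6.2 and Figure 2 |
|---|---|---|---|---|
| Borderline | Definite mild | Definite mild | Worse | No side-by-side reading (not Group A); latent in Figure 2, so no event unless the any-time clause applies |
| Borderline | Borderline | Definite mild | Worse | No side-by-side reading (not Group A); depends on the any-time clause |
| Borderline or definite mild | Severe | – | Worse | Event through Figure 2 |
| Borderline | Normal | Borderline | None | Side-by-side reads worse: event |

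**Readings of the any-time clause**

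1. Any echocardiographic RHD after entry: persistent latent disease would be an event, which contradicts Figure 2.
2. RHD after a normal echo: only children who normalised can have the event, and years 0–2 progression is still missed.
3. A category worse than at entry: this closes the gap, but the plan does not say it and Table 6 names only the side-by-side result.

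**Children affected** (section 3.4: 364 normal, 415 persistent latent)

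- Total: 364 + 415 = 779. This leaves out any child already Severe or lost by year 2.
- No defined side-by-side reading: 415/779 = 53.3%.
- Able to relapse from normal: 364/779 = 46.7%. At the plan's assumed 3% for Group A, 0.03 × 364 = 10.9, about 11 events, or 10.9/779 = 1.4 percentage points of all children. Those who only return to their entry category are no worse than at randomisation.

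**Early effect retained** (assumed rates; the plan gives none)

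If only Severe at year 2 is counted, the retained difference is f × (control − BPG), where f is the share of years 0–2 progression that reaches Severe.

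| Assumed progression, control v BPG | True difference | f = 10% | f = 25% | f = 50% |
|---|---|---|---|---|
| 5% v 1% | 4 points | 0.4 | 1.0 | 2.0 |
| 10% v 2% | 8 points | 0.8 | 2.0 | 4.0 |
| 15% v 5% | 10 points | 1.0 | 2.5 | 5.0 |

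The share lost is 1 − f. It is zero if the any-time clause is read in sense 3.

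**Sign of the contrast**

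Suppose the side-by-side reading were extended to latent children and Severe at year 2 were ignored. The BPG minus control difference is then (difference in share normal at year 2) × (relapse risk − late progression risk).

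- Assumed 46% v 42% normal, relapse 10%, late progression 3%: 0.04 × 0.07 = +0.28 points.
- Relapse at the plan's 3% with late progression also 3%: 0.04 × 0 = 0.
- Equal shares normal: 0, whatever the other risks.
- First set, plus an assumed 1% v 0% Severe at year 2: 0.28 − 1 = about −0.7 points.

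With the entry echo as reference, the first set and assumed early progression of 6% v 1% give control 6% + 52% × 3% = 7.56% and BPG 1% + 53% × 3% = 2.59%, a difference of −4.97 points.

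**The case against.** The strongest reply is the any-time clause. If it was meant to count any category worsening since GOAL entry, no early progression is lost. That reading is possible, but the clause has no stated reference echo and Table 6 leaves it out. What stands is that the outcome is undefined on this point, not that a loss is proven.

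A second reply is that the Group A restriction in section 5 may serve only to separate Group A from Group B, so that children in Aim 2 might also be read side by side. The plan describes no such reading for Aim 2, whose outcome comes from another variable. Even if it were done, the pair would still be year 2 against year 5, and the child who became definite mild by year 2 and stayed there would read as the same.

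Third, counting relapse after a normal echo may be intended: section 6.2 opens with a comparison within Group A, and the clinical question in section 2.1 concerns children who have normalised. That is a legitimate question, but it differs from the five-year effect of allocation at GOAL entry.

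A reader might also infer that most of the early progression is lost, or that the result would turn against BPG. The plan supports neither. It gives no years 0–2 rates and no Severe share. A change of sign needs more normal echoes under BPG and a relapse risk above the late progression risk, and section 3 reports no difference in normalisation between the arms.

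**Conclusion.** The mismatch is in the text and does not depend on assumed rates: time zero is GOAL entry, the reference echo is at year 2, and the reading is specified for Group A only. On the plan's counts, 53% of the children have no defined side-by-side outcome. The any-time clause does not repair this as written.

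The likely consequence is that any benefit gained in years 0–2 is hidden or attenuated in an analysis presented as randomised. The amount cannot be worked out from the plan; the retained fractions shown are illustrations. The GOAL Trial's own operational definitions, to which section 5 refers, are not reproduced in the plan and could narrow the ambiguity. Because the analysis is exploratory, the Aim 1 primary comparison of Groups A and B is unaffected. The point should be corrected before Target-GOAL is analysed.

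**What to change.** In section 6.2 and Table 6, define the Target-GOAL event for all randomised children as confirmed ARF, or a diagnostic category at year 5 worse than the category on the GOAL enrolment echo, using the category-change rule in section 5. If the any-time wording is kept, apply the same rule to every earlier echo. State that Severe at year 2 remains an event, as in Figure 2, and how that category maps to definite moderate/severe.

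Take the entry category from the stratification variable. Because it records only borderline or definite, confirm from the existing echo readings that definite can be split into mild and moderate/severe. Report the year-2 to year-5 side-by-side result separately, as a description of Group A.

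The cost is wording and programming. Tables 1 and 2 already schedule a final echo for both aims, so no new imaging is needed. The downside is that the outcome would rest on category readings instead of paired, order-blinded images.
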